We have developed a preliminary model of BMT group medical visits, conducted focus groups with BMT patients and providers, and we will use this data to develop a manualized group-based BMT intervention (G-BMT). We will then conduct an RCT of the G-BMT intervention within primary care to preliminarily test its efficacy, acceptability, and feasibility. Participants who have persistent opioid abuse while receiving BMT in primary care will be randomized to the G-BMT intervention (40 participants in 5 groups) or to intensify BMT (treatment as usual) with their individual primary care physician (40 participants). The specific aims for this developmental study include:

Aim 1: To develop the G-BMT intervention for primary care

[name] G-BMT 2-6-18

We will adapt a preliminary model of BMT group medical visits to meet the needs of opioid users with persistent opioid abuse.

Aim 2: To pilot test G-BMT for efficacy, acceptability, and feasibility in an RCT within primary care H1: In a 16-week RCT of G-BMT, participants who receive the G-BMT intervention (vs. treatment as usual) will have higher abstinence rates (primary outcome, efficacy), fewer HIV risk behaviors (efficacy), and greater satisfaction with treatment (acceptability) and adherence to medical visits (feasibility).

II. Background and Significance

In 2010, drug overdose replaced motor vehicle accidents as the leading cause of accidental death in the United States.³⁴ This epidemic has primarily been driven by opioid addiction, with opioid analgesic use, misuse, and overdose tripling between 1999 and 2010.¹ Opioid analgesic overdose deaths reached nearly 17,000 in 2010, the latest year that data is available, while heroin overdoses likely cause an additional 2,000 deaths annually.^{3,35} As regulations regarding opioid analgesic prescribing have become more restrictive, heroin use and overdose have also seen increases. In New York City, between 2011 and 2012, opioid analgesic overdose deaths decreased by 12%, while between 2010 and 2012, heroin overdose deaths increased by 71% and remain the leading cause of drug overdose death.³⁶ In the United States, opioid addiction is a public health crisis with its epicenter in New York City.

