Peer support: Therapeutic groups are a mainstay of addiction treatment because they offer drug users, who are often socially isolated, validation and support from others with similar experiences. The behavioral specialist will facilitate conversation about current opioid use, goals for recovery, and triggers for relapse. We anticipate this will take 20-25 minutes.

Medical Management: Each visit will end with guided relaxation and meditation as a way to calm any heightened emotions from group interactions. The physician will write prescriptions for BMT and address individual concerns (e.g., changes in buprenorphine dosage). Because group medical visits will replace most individual visits, focused histories and physical exams may be necessary and could occur in a private room as needed. If more attention is required for acute symptoms an individual visit can be scheduled at the CHC.

Interaction between primary care physicians (PCPs) and research team: The protocol for communications with referring PCPs will be as follows: 1) G-BMT participants will sign a treatment agreement stating that they will attend group visits weekly and all medication refill requests will go to the group physician; 2) the group physician will send electronic medical record (EMR) messages to the PCP with updates to the treatment plan following each group visit; 3) participants will continue to see their PCP for acute medical care, but not for BMT during the study period; and 4) the group physician will transfer care back to the PCP following completion of the G-BMT intervention through an in-person conversation. The treatment agreement (see appendix), which includes patient and provider expectations, and specifies that all prescriptions will be written at BMT group medical visits, will be discussed at the first group visit and signed by both patients and the G-BMT physician. Subsequently, PCPs will be asked to read and sign the agreement as well. Because this study is developmental, deviations from the agreement (e.g. asking the PCP for a prescription refill following a missed group visit) will be recorded as an outcome for future adaptations to the protocol.

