- a.) *Retention in treatment* will be used to determine whether participants remain in BMT following the specified time intervals. *Three month retention* will be defined as having a medical visit or active

buprenorphine prescription 12-16 weeks after study initiation (one month after G-BMT intervention completion). *Six month retention* will be assessed at 24-28 weeks after study initiation.

b.) *Changes in HIV risk behaviors* will be based on the AIDS risk inventory, which includes questions regarding frequency of injection drug use, number of times sharing syringes, number of sexual partners, and frequency of unprotected sex. We will assess risk behaviors at completion of the G-BMT intervention (8 week visit) and two months following completion of the intervention (16 week visit).

Primary outcome (acceptability): Overall satisfaction with BMT will be measured on a 5-point Likert scale for participants and providers.

Primary outcome (feasibility): We will compare *medication and visit adherence* between the G-BMT and TAU arms as the primary measure of feasibility. Medication adherence will be determined from medical record data based on lapses in BMT defined as the number of days without an active buprenorphine prescription during the study. Visit adherence will be defined as the proportion of obligated medical visits (as per G-BMT or TAU protocol) attended. Other important measures of feasibility are listed in Table 2 and will be used as secondary outcomes and to assess fidelity to the G-BMT intervention.

G-BMT component	Measure	Assessment
Overall	Participant engagement # urine drug tests collected Time per group medical visit	RA conducted EMR Timed
Buprenorphine Education	Fidelity to intervention Time for education	Checklist Timed
Self-management skills	Self-assessment forms Fidelity to intervention Time for instruction	Collected Checklist Timed
Peer Support	Personal Updates Feedback to other participants Group Cohesion Time for facilitated discussion	RA observed RA observed GCQ-S* Timed
Medication Management	# non-BMT medical complaints # individual physical exams Time for medical management	EMR RA observed Timed
*assessed as part of ACASI interviews		

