Outcome Measures: **Primary outcome (efficacy):** we will use a dichotomous measure (yes/no) of *opioid abstinence* based on 30-day self-reported opioid use following completion of the intervention and the results of urine drug tests (opiates, methadone, oxycodone) at the 8 and 12 week research visits. Missing urine drug tests will be considered to be positive for opioids.

Secondary outcomes (efficacy): 1.) *Retention in treatment* will be used to determine whether participants remain in BMT following the specified time intervals. *Three month retention* will be defined as having a medical visit or active buprenorphine prescription 12-16 weeks after study initiation (one month after G-BMT intervention completion). *Six month retention* will be assessed at 24-28 weeks after study initiation.

2.) *Changes in HIV risk behaviors* will be based on the AIDS risk inventory, which includes questions regarding frequency of injection drug use, number of times sharing syringes, number of sexual partners, and frequency of unprotected sex. We will assess risk behaviors at completion of the G-BMT intervention (8 week visit) and two months following completion of the intervention (16 week visit).

Primary outcome (acceptability): Overall satisfaction with BMT will be measured on a 5-point Likert scale for participants and providers.

Primary outcome (feasibility): We will compare *medication and visit adherence* between the G-BMT and TAU arms as the primary measure of feasibility. Medication adherence will be determined from medical record data based on lapses in BMT defined as the number of days without an active buprenorphine prescription during the study. Visit adherence will be defined as the proportion of obligated medical visits (as per G-BMT or TAU protocol) attended. Other important secondary outcomes will be measures of feasibility from assessments of fidelity to the G-BMT intervention based on audio-recordings and observations of the group medical visits.

Inclusion/exclusion criteria: 1) Currently receiving BMT at the CHC; 2) Received BMT for ≥ 12 weeks; 3) Persistent opioid abuse (urine drug testing positive for an unprescribed opioid in the previous 6 months); 4) ≥ 18 years old; 5) fluent in English or Spanish. Pregnant women and patients who show contraindications to BMT (alcohol use disorder; benzodiazepine use disorder; unstable mental health condition) will be excluded.

TRIAL MANAGEMENT

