Stress imposed on participants due to group participation: There will be a board certified physician and behavioral specialist at each group medical visit. Drs. [name] and [name] will also be available to intervene if participants express high levels of distress during group medical visits. Drs. [name] and [name] will review audio recordings of group sessions and have regular meetings with study clinicians to inquire about distress or conflict during group sessions.

Continuing BMT despite ongoing opioid abuse: We are selecting for a population with persistent opioid abuse, and these individuals may need a higher level of treatment intensity than can be offered in primary care settings.

Burden of attending an increased number of medical visits following intensification of BMT: Participants randomized to the G-BMT intervention will be expected to attend weekly group visits during the 8 week intervention. Participants randomized to the TAU arm will also likely be required to attend an increased number of medical visits, because PCPs will follow an intensification of BMT protocol that instructs them to increase visits to twice monthly or weekly if participants continue to abuse opioids. The increased number of visits could be burdensome and negatively affect adherence to buprenorphine treatment if participants missed medical visits and had lapses in their buprenorphine prescriptions.

Recruitment and informed consent: We will obtain informed consent for all participants of the RCT prior to collecting any information with personal identifiers (e.g. locator form or medical record release forms), administering the baseline ACASI interview, and randomization to an intervention arm. Informed consent will be obtained by the RA.

Protection against risk: We will institute the following processes to ensure confidentiality is maintained:

We will create a system that prevents linking sensitive material to participants' personal identifiers. We will have a "name-based" system and "ID-based" system that will remain all documents that have patient identifiers will be filed together. Some of these documents will have participants' signatures (e.g. consent forms) and others will have personal information (e.g. locator forms).

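### Treatment intensity is counted differently in each arm, so neither version supports the exploratory mediation analysis; the window for visit adherence should also be stated

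*Combined protocol and SAP*

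**What the plan says.** **Intensity.** Section III, Data sources and measures, Medical records, defines observed intensity by arm. In TAU it is the number of medical or counseling visits made over the study period. In G-BMT it is a tally of group visits only. Treatment as usual reserves the variable for exploratory analyses, and the section III Analysis paragraph lists it as a candidate mediator of the effect on abstinence, to be examined through interactions with study condition. The Data analysis plan in section IV gives a different mediator, intensity of the intervention, specified as group sessions attended, again with an interaction.

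G-BMT participants are "expected to attend weekly group visits during the 8 week intervention", which is 8 visits. Those visits are not all of their care. The Medical Management paragraph begins "Because group medical visits will replace most individual visits", which leaves some individual visits in place, and under the arrangements with primary care physicians (PCPs) "the group physician will transfer care back to the PCP following completion of the G-BMT intervention through an in-person conversation".

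**Visit adherence.** Medication and visit adherence are compared "between the G-BMT and TAU arms as the primary measure of feasibility". The definition is "Visit adherence will be defined as the proportion of obligated medical visits (as per G-BMT or TAU protocol) attended", and section IV, Outcome Measures, repeats it. Neither place names weeks. Medication adherence is "the number of days without an active buprenorphine prescription during the study", the same stated period in both arms. Table 1 lists medical visits for weeks 1-16 and clinical urine tests for weeks 1-8.

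**The concern.** A mediator has to be the same quantity in both arms. The question is whether G-BMT works, if it does, because patients receive more contact. If the count admits different visit types by arm, part of the arm difference in the mediator comes from the definition. A variable that is zero by design throughout TAU says nothing about intensity there. The trial is meant to inform a larger one, so a mistaken conclusion about contact versus group format could be carried forward.

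Visit adherence is one of the two components of the primary feasibility comparison, and H1 predicts that it is better with G-BMT. With no stated window, the denominator can be built in more than one way, and some of those ways would let calendar time enter the arm comparison.

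**Working it through.** **Design figure.** The plan gives no number for either visit measure. Its one design figure is the 37% detectable abstinence rate. With 40 per arm, a 10% control rate and a design effect of 1 + (8 - 1) x 0.01 = 1.07, the effective size is 40/1.07 = 37.4 per arm. With pooled variance and two-sided 5% (alpha is not stated, so this is assumed), the rate giving 80% power is 37.06%. It reproduces and uses neither visit measure.

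**1. Observed intensity (Medical records).** Suppose a G-BMT participant attends 8 group visits, 2 monthly PCP visits after hand-back and 4 counseling visits, and that the study period means 16 weeks.
- Actual visits: 8 + 2 + 4 = 14. Score: 8.
- A TAU participant with 14 medical and counseling visits scores 14.
- True difference: 0. Recorded difference (G-BMT minus TAU): 8 - 14 = -6.

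The interaction is estimable here, but its two slopes are per group visit in one arm and per medical or counseling visit in the other.

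**2. Group sessions as mediator (section IV).** Let A = 1 for G-BMT and 0 for TAU, and let M be group sessions attended. With TAU treated as assigned, M = 0 whenever A = 0, so A x M = M for every participant. Then

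logit P(abstinent) = b0 + b1 A + b2 M + b3 (A x M) = b0 + b1 A + (b2 + b3) M.

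Only the sum b2 + b3 can be estimated. Without the interaction, b1 compares TAU with a G-BMT participant who attended no sessions.

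**3. Visit adherence, if the windows differed.** This is an illustration, because the documents give no attendance rates. Assume the same attendance in both arms: p1 in weeks 1-8 and p1 - d in weeks 9-16. Score G-BMT on 8 visits in weeks 1-8 and TAU on weeks 1-16, and let w be the share of obligated TAU visits in weeks 9-16. Then G-BMT = p1, TAU = p1 - d x w, and the spurious difference is d x w. The schedules follow the step-up rules under Treatment as usual, with the first visit assumed at week 4.

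| TAU schedule (visit weeks) | w | d = 25 | d = 15 | rise of 10 |
|---|---|---|---|---|
| Step-up, then referred out (4, 6, 7) | 0/3 = 0 | 0 | 0 | 0 |
| Monthly (4, 8, 12, 16) | 2/4 = 0.50 | 12.5 | 7.5 | -5.0 |
| Twice monthly (4, 6, ..., 16) | 4/7 = 0.57 | 14.3 | 8.6 | -5.7 |
| Weekly continuing (4, 6, 7, ..., 16) | 8/12 = 0.67 | 16.7 | 10.0 | -6.7 |

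With flat attendance the difference is 0 throughout.

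**4. What a common window does.**
- Weeks 1-8 in both arms gives 0 in every cell above, because the model puts the only change at week 8.
- With a steady fall from 75% (week 1) to 50% (week 16), or 25/15 = 1.667 points per week, G-BMT averages week 4.5 and scores 75 - 3.5 x 1.667 = 69.2%. Monthly TAU over weeks 1-16 averages week 10 and scores 60.0%, a gap of 9.2. Over weeks 1-8 it averages week 6 and scores 66.7%, a gap of 2.5.
- Weeks 1-16 in both arms, with 2 monthly PCP visits counted for G-BMT after week 8, gives G-BMT a late share of 2/10 = 0.20. For monthly TAU and d = 25 the gap is 25 x (0.50 - 0.20) = 7.5, against 12.5. If TAU is referred out early it is 25 x (0 - 0.20) = -5.0, against 0.

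**The case against.** **On intensity.** A group visit combines physician care and behavioral counseling, so medical or counseling visits are a reasonable TAU counterpart. A common tally scores a 90-minute group session the same as one counseling contact. Interactions also allow a separate slope in each arm. The point about weighting stands as a cost of the fix. Separate slopes do not rescue a mediator that means different things by arm, and in the section IV version the TAU slope cannot be estimated at all. It is also fair that zero is the correct TAU value for exposure to G-BMT. That makes group sessions a sound dose measure within the arm, but not a between-arm mediator.

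The meaning of the study period is open too. The paragraph on interaction with PCPs uses the phrase in a way that could mean the 8-week intervention. The 14-visit example would then shrink, but the difference in visit types would remain.

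**Two stronger readings.** A reader might infer that the plan fixes visit adherence at weeks 1-8 for G-BMT and weeks 1-16 for TAU, and so favors G-BMT. The documents do not support that. No window is written. The monthly minimum under Treatment as usual is worded for all BMT patients with persistent opioid use, and G-BMT participants return to their PCPs, so a common 1-16 reading is available and fits the single Table 1 row for medical visits. The clinical urine row, weeks 1-8 with no intervention-only mark, ties TAU visits to weeks 1-8 for at least one measure. The direction of any bias also depends on an unknown attendance trend.

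A reader might also infer that the judgment on the ideal number of visits is spoiled. That passage, under Additional adaptations, concerns the number of G-BMT visits, for which group sessions attended is the right measure.

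**Conclusion.** The intensity point holds on the text. Observed intensity counts different visit types by arm and is capped at 8 in G-BMT. The section IV mediator is zero for TAU participants treated as assigned, so its interaction with study condition cannot be separated from the mediator. That second result is algebraic and needs no attendance assumption; only TAU participants who attended groups would break it. The size of the first depends on how many visits G-BMT participants make outside the groups, which the documents do not give. The consequence is confined to exploratory analyses.

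The visit-adherence point is that the window is unstated; a mismatch is not shown. If the windows did differ, the artifact would run from -6.7 to 16.7 points under the assumptions above, including 0. It touches a feasibility measure only. This is a low-severity improvement; the abstinence definition, the 37% figure and the stopping rules do not depend on it.

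**What to change.** **Intensity.** In Medical records, Analysis and the section IV Data analysis plan, define one mediator: group, medical and counseling visits attended over the same weeks in both arms. Weeks 1-12 would suit, since week 12 is the last research visit in the abstinence outcome. Report the count by visit type as well, because group and counseling visits otherwise weigh equally. Keep group sessions attended as a within-G-BMT dose measure, including for the question of how many visits G-BMT should have.

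**Visit adherence.** State the weeks and the obligated visits for each arm, and report the comparison over a common window. Weeks 1-8, with weeks 9-16 shown separately, is one option. TAU may then have as few as 2 obligated visits, so individual scores would be 0, 50 or 100%. Weeks 1-16 avoids that but leaves the arms with different shares of late visits. Under either, the TAU denominator still varies with urine results, while the G-BMT group-visit obligation stays at 8.

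**Cost.** A few sentences in an amendment and no change to care. Medical and counseling visits are already to be extracted and the research assistant already records group attendance, so no new data are needed. Counseling outside the health system would still be missed in both arms.

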Provider Satisfaction: We will adapt a previously published questionnaire to assess acceptability of the intervention to participants' PCPs. Satisfaction will be measured in three areas: overall satisfaction with BMT, perceived effectiveness of BMT intensification and support for BMT at the CHC.¹⁰¹ We will add items for PCPs with patients randomized to the G-BMT intervention to assess satisfaction with communications with the G- BMT team and likelihood of referring patients to group-based BMT in the future.

Table 1. Timing and delivery of intervention and study measures

Measure	Study Instrument	Domain	Assessment Period (week)
Urine			
Opioid use	Observed urine	-	All [†]
Questionnaires			
Sociodemographic information	BHIVES Study ⁸²	-	0
HIV Risk Behaviors	AIDS risk inventory ⁹³	-	0, 8, 16
Self-reported drug use	Addiction Severity Index ⁹⁴	-	All
Depression	CES-D ⁹⁵	-	0, 8, 16
Self-efficacy	DTCQ-8 ⁹⁶	Self-efficacy	0, 8, 12, 16
Social Support	MSPSS ⁹⁷	Outcome Expectation	0, 8, 12, 16
Buprenorphine Knowledge	10 item questionnaire	Knowledge	0, 8, 16
Quality of Life	SF-12 ⁹⁸	-	0, 8, 16
Group cohesion*	GCQ-S ⁹⁹	-	2, 4, 8
Medical Records			
Medical Visits	-	-	1-16
Buprenorphine prescriptions	-	-	1-16
Referrals	-	-	1-16
Opioid use	Clinical urine		1-8
Retention in care	-	-	0, 12, 24
Intervention Materials			
Chronic Health Conditions	-	-	0
Self-assessment forms	Check-list	Goals	1-8
Intervention fidelity	Check-list	-	1-8
Post-intervention Questionnaires			
Patient satisfaction	PCBSS ¹⁰⁰	Barriers and Facilitators	8
Provider satisfaction	5 item questionnaire ¹⁰¹	-	8
Qualitative Interviews*	Interview Guide		8

*only collected for intervention arm; [†]Study visits (2,4,6,8,12,16 weeks) CES-D = Center for Epidemiologic Studies Depression Scale; DTCQ-8 = Drug-Taking Confidence Questionnaire, 8 item version; MSPSS = Multidimensional Scale of Perceived Social Support; SF-12 = SF-12 Health Survey; GCQ-S = Group Climate Questionnaire – Short Form; PCBSS = Primary Care Buprenorphine Satisfaction Scale

Analysis:

Main outcome variables:

Primary outcome (efficacy): we will use a dichotomous measure (yes/no) of *opioid abstinence* based on 30-day self-reported opioid use following completion of the intervention and the results of urine drug tests (opiates, methadone, oxycodone) at the 8 and 12 week research visits (see Figure 1). Missing urine drug tests will be considered to be positive for opioids.

Secondary outcomes (efficacy):

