Analysis: We will use mixed effects logistical regression models incorporating different correlation structures between study arms to account for clustering by group in the intervention arm and by PCP in the TAU arm. For the primary outcomes, abstinence will be the dependent variable and study condition will be the main independent variable. Models will include key covariates that are not equally distributed between study arms.

For each secondary outcome, we will construct a separate mixed effects linear or logistic regression model. In other exploratory analyses, we will determine whether changes in perceived social support or self-efficacy, or the *observed intensity* of BMT mediate the association between study condition and abstinence by using interaction terms for key variables and study condition.

Qualitative Analysis: Analytic Plan. Using NVivo software, analysis of qualitative data will be conducted using a modified grounded theory approach. We will develop a coding scheme that reflects the themes that emerge upon iterative reading of the transcriptions. In grounded theory, themes are not specified prior to analysis, but our modified approach will use the framework of Social Cognitive Theory to organize the themes. With the first 3-5 interviews, preliminary codes will be developed independently by [name] and the RA. Using the constant comparative method, additional readings of the transcriptions will lead to consolidation of these coding schemes until no further refinement is required. Coding discrepancies will be resolved by consensus. Once coded, these themes will be organized into a conceptual model explaining the impact of group buprenorphine maintenance treatment.

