Data entry method: At enrollment, the RA will administer interviews using ACASI technology. Interview data will be directly entered on a lap top computer, which will be password protected, and will contain only participant study ID (no other identifying information). Additional data (e.g. urine drug test results) will be entered into a password-protected Redcap database by two separate, trained data entry staff, and discrepancies will be corrected by [name] based on source documents.

Data analysis plan: We will use mixed effects logistical regression models incorporating different correlation structures between study arms to account for clustering by group in the intervention arm. For the primary outcomes, abstinence will be the dependent variable and study condition will be the main independent variable. Covariates will include depressive symptoms and sociodemographic variables that are associated with the study condition in bivariate testing. For each secondary outcome, we will construct a separate mixed effects linear or logistic regression model with similar adjustments. In other exploratory analyses, we will determine whether changes in perceived social support or self-efficacy, depressive symptoms, or intensity of the intervention (i.e. # of group sessions attended) mediate the association between study condition and abstinence by using interaction terms with these variables and study condition. We will also determine whether sub-groups of patients (e.g. those with low perceived social support) benefit most from group participation.

QUALITY ASSURANCE

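### The week-0 HIV-risk value is collected but is not a pre-specified covariate in the HIV-risk models, which gives up precision

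*Combined protocol and SAP*

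**What the plan says.** H1 under Aim 2 (section I) lists reduced HIV risk behaviour among the efficacy claims. Under Secondary outcomes (efficacy), the outcome is "Changes in HIV risk behaviors", taken from the AIDS risk inventory, which covers "frequency of injection drug use, number of times sharing syringes, number of sexual partners, and frequency of unprotected sex". It is assessed at the 8-week and 16-week visits. The Table 1 row "HIV Risk Behaviors" adds a week-0 measurement.

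The analysis is described twice:

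- **Section III, Analysis.** In the paragraph on the primary outcome: "Models will include key covariates that are not equally distributed between study arms". The next paragraph gives each secondary outcome "a separate mixed effects linear or logistic regression model" and says nothing of its own about covariates.
- **Section IV, Data analysis plan.** "Covariates will include depressive symptoms and sociodemographic variables that are associated with the study condition in bivariate testing". Secondary outcomes get the same model types with similar adjustments.

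Neither section names the baseline value of the outcome as a covariate. Neither says whether change is analysed as a difference from week 0 or in some other way.

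**The concern.** In a randomised trial, differences between arms at baseline arise by chance. A rule that adjusts only for variables that happen to differ selects on the wrong property: a covariate improves precision because it predicts the outcome, not because it is imbalanced. The earlier value of the same measure is the natural candidate, and here it is already collected.

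Under the section III rule, baseline HIV risk enters only if it is judged unequal between arms. The section IV rule names depressive symptoms and sociodemographic variables, and baseline HIV risk is neither. If the section IV bivariate testing were run at the 5% level (no level is stated) and HIV risk were admitted as a candidate, a randomised baseline variable would pass about one time in twenty.

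Precision is at stake. The Power Analysis says that the trial may be too small for its primary outcome, and that estimating an effect size for a later trial matters more. With 40 per arm, precision that needs no extra participants or visits is worth having.

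**Working it through.** **1. The plan's own power figure.** The only one concerns abstinence: 10% in control, 37% detectable, 40 per arm, ICC 0.01, 80% power. Groups average 8, so the design effect is 1 + (8 − 1) × 0.01 = 1.07 and the effective n is 40/1.07 = 37.4 per arm. With a pooled two-sided test at 0.05 (alpha and sidedness are assumed, as neither is stated), the detectable rate is 37.1% and power at 37% is 79.9%. The figure reproduces. It does not concern HIV risk, for which no power figure, SD or correlation is given.

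**2. Relative variance of the treatment effect.** Let r be the correlation between the week-0 and follow-up values, with equal variances at both times and in both arms. Relative to an analysis of follow-up values alone:

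- follow-up only: 1
- unadjusted change score: 2(1 − r)
- follow-up adjusted for week 0: 1 − r²

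Adjustment is at least as good as either alternative: 1 − (1 − r²) = r², and 2(1 − r) − (1 − r²) = (1 − r)². Neither is negative.

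**3. Size, with r assumed.** Against a change score the variance ratio is (1 − r²)/[2(1 − r)] = (1 + r)/2. The equivalent gain in participants is the inverse of the ratio, minus 1.

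| r (assumed) | Change score | Adjusted | Cut vs change score | Equivalent extra participants | Cut vs follow-up only |
|---|---|---|---|---|---|
| 0.3 | 1.40 | 0.91 | 35% | 1/0.65 − 1 = 54% | 9% |
| 0.5 | 1.00 | 0.75 | 25% | 1/0.75 − 1 = 33% | 25% |
| 0.7 | 0.60 | 0.51 | 15% | 1/0.85 − 1 = 18% | 49% |

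At r = 0.5, 80 adjusted participants give the precision of 80/0.75 ≈ 107 unadjusted.

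**4. Detectable difference.** In SD units at 80% power it is 2.80 × √(2 × 1.07/40 × V), where V is the relative variance and the abstinence design effect is borrowed as an assumption. Follow-up only gives 0.65 SD throughout. For r = 0.3 / 0.5 / 0.7, the change score gives 0.77 / 0.65 / 0.50 SD and the adjusted analysis 0.62 / 0.56 / 0.46 SD.

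**5. Does the model family matter as well?** Zero-heavy counts were simulated with 40 per arm, no clustering, 2000 runs per scenario, an assumed mean of 5 among those at risk, and that rate halved by treatment. Size-corrected power uses the cut-off that gives 5% rejection under no effect.

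| Zeros (assumed) | Power: linear change | Power: linear adjusted | Power: adjusted count | Type I error: count | Size-corrected: linear adjusted | Size-corrected: count |
|---|---|---|---|---|---|---|
| 50% | 25% | 39% | 54% | 8% | 42% | 44% |
| 67% | 17% | 24% | 40% | 10% | 27% | 26% |
| 83% | 9% | 11% | 30% | 15% | 15% | 15% |

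Moving from the change score to baseline adjustment raises power in every scenario. The count model's apparent further gain largely disappears once its inflated type I error is corrected.

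**The case against.** The strongest reply is that the outcome is defined as change, so baseline is already used by subtraction, and that the section III rule could admit baseline risk if the arms differ. Both points are right, and they limit the claim. Adjustment is not pre-specified; it is not ruled out. A reader might infer that baseline information goes wholly unused and quote the 49% cut at r = 0.7, equivalent to 1/0.51 − 1 = 96% more participants. That compares adjustment with an analysis ignoring week 0, which a change outcome does not do. Against a change score the figures at r = 0.7 are 15% and 18%, and the gain shrinks as r rises.

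A reader might also infer that these outcomes are zero-heavy counts needing a negative binomial model. The documents do not establish this. Eligibility requires no injection, sharing or sexual risk, so zeros are plausible, but no zero share is given. Two of the four items are numbers of events or partners. The other two are frequencies with no response scale and could be ordinal. The simulation shows no dependable power advantage for a count model at this size, and type I error of 8% to 15% without a small-sample correction.

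Nor does the point extend to medication adherence, measured as "the number of days without an active buprenorphine prescription during the study". That is a primary feasibility measure, whereas the quoted model sentence covers secondary outcomes. Table 1 lists prescriptions from week 1, so there is no week-0 value to adjust for.

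Finally, the stakes are low: a secondary outcome in a pilot that makes no power claim for it. That stands, and it sets the weight of the point.

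**Conclusion.** The point holds as a minor but free improvement. The week-0 HIV-risk value is collected, yet neither analysis section commits to using it as a covariate, and both tie adjustment to observed differences between arms. For assumed correlations of 0.3 to 0.7, committing to it lowers variance by roughly 15% to 35% against the unadjusted change score that the outcome definition suggests.

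These figures rest on assumed correlations, equal variances and a linear model. They ignore the small cost of estimating the covariate's coefficient. They do not carry over directly to an item analysed by logistic regression, where adjustment also changes the odds ratio being estimated. The planned linear or logistic models are not shown to be invalid; whether they fit cannot be judged until item scoring is stated.

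**What to change.** In section III (Analysis) and section IV (Data analysis plan), state that the mixed model for the week-8 and week-16 values of each HIV-risk measure includes that measure's week-0 value as a covariate, regardless of observed imbalance. Keep the clustering terms already planned, and make the covariate rule the same in both sections. State how each inventory item is scored and which items get the linear or the logistic model; for a dichotomised item, use its week-0 status.

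A count or two-part model can be named as an optional sensitivity analysis, with small-sample or permutation inference.

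The cost is analysis wording only. No participants, visits or measurements are added, and each model estimates one more coefficient.
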